### 6.2 Shipment, Storage and Handling

TBS and MVA-BN-RSV vaccine are packed separately and will be shipped temperature controlled and monitored to the CTS (if applicable via a warehouse). At the CTS, the package is handed over to the personnel in charge of vaccine preparation, e.g. the pharmacist. After receipt the CTS personnel are responsible for proper storage of vaccine and diluent.

MVA-BN-RSV vaccine is shipped and stored frozen at  $-4^{\circ}\text{F} \pm 9^{\circ}\text{F}$  ( $-20^{\circ}\text{C} \pm 5^{\circ}\text{C}$ ) avoiding direct light. A vial must not be re-frozen once it has been thawed. Details on shipment, storage and handling of the LF formulation of MVA-BN-RSV vaccine are provided in BN Standard Operating Procedure (SOP) [REDACTED]

[REDACTED]  
[REDACTED] (see also [Section 6.3](#)).

TBS has to be shipped and stored refrigerated at 36°F to 46°F (+2°C to +8°C).

### **6.3 Preparation, Administration and Dosage**

Details on vaccine storage, preparation and administration of MVA-BN-RSV vaccine are provided in [REDACTED]  
[REDACTED]  
[REDACTED]

Study specific vaccination instructions detailing the preparation/dilution and application procedure and handling of TBS will be provided to the CTS.

### **6.4 Accountability and Disposal**

After receipt of the IMP, the CTS personnel have the ultimate responsibility for distribution, proper storage and drug accountability. Records of receipt, inventory, use by each subject, return or disposal and temperature control must be maintained in the pharmacy file.

Used and unused vials must be stored in a safe place and remain the property of BN. The personnel of the respective CTS are responsible for ensuring adequate accountability of all used and unused IMP. This includes acknowledgement of receipt of each shipment of IMP (quantity and condition) and IMP accountability using an IMP inventory log. The IMP inventory log will document the quantity of IMP received, quantity of IMP used for vaccination (including lot number, date dispensed, subject identification number and initials of the person dispensing the IMP) and quantity of IMP returned to BN or destroyed.

Additionally, the quantity of IMP returned to BN or destroyed must be documented on an IMP return/destruction form. If destruction at the CTS is agreed upon, material should be autoclaved or incinerated and discarded according to local regulations.

Furthermore, used syringes/ancillary supply should be autoclaved or incinerated and discarded at the CTS according to local regulations.

## **7 Assessment of Immunogenicity**

The immunogenicity of the vaccine will be assessed by measuring humoral, cellular and mucosal immune responses on collected serum, nasal swab and PBMC samples.

- RSV-specific, G protein A strain-specific, G protein B strain-specific systemic antibody levels will be determined from serum samples using IgG/IgA ELISAs. Further, two

separate PRNTs will be performed to measure neutralizing antibody levels to RSV strains A and B.

- RSV-specific mucosal antibody levels will be determined from nasal swab samples using an RSV-specific IgA ELISA.
- IFN- $\gamma$  and IL-4 secreting, RSV-specific T cells will be quantified using an ELISPOT assay on PBMC samples.
- RSV-specific Memory B cells will be measured on PBMC samples obtained at the (B)FU visits and compared between treatment groups

All immunogenicity testing will be performed at Bavarian Nordic GmbH, [REDACTED] Testing SOPs, effective at the time of testing will be filed in the electronic Trial Master File.

The procedures for collection, preparation, storage and shipment of specimens for immunogenicity testing (i.e. serum, nasal swabs and PBMC) are specified in separate Study Specific Instructions, which will be provided to the investigators / clinical trial site personnel as well as to the processing laboratories before recruitment commences. Additionally, the procedures will be trained during the investigator meeting / site initiation visit.

## 7.1 Systemic Humoral Immune Responses

Serum samples will be collected as outlined in the trials procedure schedule in [Section 1.6](#).

All samples for immunogenicity testing obtained on vaccination visits will be collected prior to vaccination.

The procedures for the immunogenicity tests performed are outlined in [Sections 7.1.1](#) and [7.1.2](#) below.

### 7.1.1 RSV-specific ELISA

RSV-specific IgG/IgA antibody responses will be determined using several ELISAs. Details of the procedure are defined in the SOP [REDACTED] “ELISA to determine RSV-Specific Antibody Titers (IgG) in Human Serum Samples”, SOP [REDACTED] “ELISA to determine RSV-Specific IgA Titers in Human Serum Samples”, SOP [REDACTED] “ELISA to determine RSV G Protein (A-strain) Specific Antibody Titers (IgG) in Human Serum Samples” and SOP [REDACTED] “ELISA to determine RSV G Protein (B1-strain) Specific Antibody Titers (IgG) in Human Serum Samples”.

The individual peak titer is calculated as the maximum of all post baseline titer measurements for that individual. The individual peak titer is only missing if all post baseline titers are missing, otherwise the maximum of the available post baseline titers is used.

The GMT is calculated per visit as well as based on individual peak titers by taking the antilogarithm of the mean of the  $\log_{10}$  titer transformations. The Geometric Mean Fold Increase (GMFI) is calculated analogously per post-baseline visit as the geometric mean of the individual fold increases, i.e. the subjects' post-baseline titers at Visit X, divided by their corresponding baseline titer.

The RSV-specific antibody response rate (applicable only to post-baseline visits) is calculated per visit as well as based on individual peak titers and is defined as the percentage of subjects with antibody response based on the total number of subjects with test results available. The response status is assessed with regard to the corresponding baseline (Visit 1) test result.

### 7.1.2 RSV-specific PRNT

Two PRNTs will be performed to determine RSV-specific neutralizing antibody titers against RSV strain A and B, respectively. Details on the procedures can be found in SOP [REDACTED] (for strain A) "PRNT to determine RSV A Strain Specific Neutralizing Antibody Titers in Human Serum Samples" and [REDACTED] (for strain B) "PRNT to determine RSV B Strain Specific Neutralizing Antibody Titers in Human Serum Samples".

The individual peak titer is calculated as the maximum of all post baseline titer measurements for that individual. The individual peak titer is only missing if all post baseline titers are missing, otherwise the maximum of the available post baseline titers is used.

The GMT is calculated per visit as well as based on individual peak titers by taking the antilogarithm of the mean of the  $\log_{10}$  titer transformations. The GMFI is calculated analogously per post-baseline visit as the geometric mean of the individual fold increases, i.e. the subjects' post-baseline titers at Visit X, divided by their corresponding baseline titer.

The RSV-specific antibody response rate (applicable only to post-baseline visits) is calculated per visit as well as based on individual peak titers and is defined as the percentage of subjects with antibody response based on the total number of subjects with test results available. The response status is assessed with regard to the corresponding baseline (Visit 1) test result.

## 7.2 Mucosal Immune Responses

Nasal swab samples will be collected as outlined in [Section 1.6](#) and [Section 1.7](#). Nasal samples will be collected from both nostrils using nylon flocked swabs ([REDACTED]). Samples obtained on vaccination visits will be taken prior to vaccination. RSV-specific IgA antibody responses will be determined using an ELISA. Details of the procedure are defined in SOP [REDACTED] "ELISA to determine RSV-specific Antibody Titers (IgA) in Human Nasal Swab Samples".

The individual peak titer is calculated as the maximum of all post baseline titer measurements for that individual. The individual peak titer is only missing if all post baseline titers are missing, otherwise the maximum of the available post baseline titers is used.

The GMT is calculated per visit as well as based on individual peak titers by taking the antilogarithm of the mean of the  $\log_{10}$  titer transformations. The GMFI is calculated analogously per post-baseline visit as the geometric mean of the individual fold increases, i.e. the subjects' post-baseline titers at Visit X, divided by their corresponding baseline titer.

The RSV-specific antibody response rate (applicable only to post-baseline visits) is calculated per visit as well as based on individual peak titers and is defined as the percentage of subjects with antibody response based on the total number of subjects with test results available. The response status is assessed with regard to the corresponding baseline (Visit 1) test result.

### 7.3 Systemic Cellular Immune Responses

PBMC samples will be collected as outlined in [Section 1.6](#) and [Section 1.7](#).

Blood samples obtained on vaccination visits will be drawn prior to vaccination.

SFU per  $1 \times 10^6$  PBMC will be determined using an IFN- $\gamma$  / IL-4 ELISPOT assay using five different RSV peptide pools as well as RSV as stimulating agent. Details of the ELISPOT procedure are defined in SOP █████ “Dual Color (IFN- $\gamma$ /IL-4) RSV ELISPOT using Human PBMC”.

The geometric mean SFU/ $1 \times 10^6$  PBMC are calculated per visit.

The response rate is calculated per visit and is defined as the percentage of subjects with a response based on the total number of subjects with test results on the respective visit. The response status is assessed with regard to the corresponding baseline (Visit 1) test result.

The number of ELISPOT pools where there is a response is also calculated on a per subject basis per visit.

A subject is an ELISPOT responder to the vaccine in a particular test agent (e.g. RSV virus) if the subject has a response for at least two post baseline visits within the same test agent.

The responder rate for each test agent is the percentage of subjects who are responders to the relevant test agent out of the number of subjects with a non-missing responder status.

Furthermore, PBMC collected at the (B)FU visits will be used to determine memory B cells secreting IgG and/or IgA in an ELISPOT. Details of the procedure are defined in SOP █████ “Fluorospot to measure RSV-specific IgG/IgA secreting cells in human PBMCs”.

## 7.4 Future Use of Lab Specimen

Serum, PBMC and nasal swab samples remaining after completion of all immunogenicity testing for the trial will be stored for future testing supporting the licensure path of recombinant MVA-BN vaccines. Future testing will facilitate the bridging of trial results to animal immunogenicity results and/or to immune response data collected from subjects vaccinated with competitor vaccines. Further, remaining samples might be used for assay development and controls. Subjects will be asked to consent to storage / future use of samples and will be informed about data protection measures. Specimens will be stored in BN's secured laboratory area or at an external storage facility in a coded, pseudonymized manner to ensure data protection. Genetic testing will not be performed.

## 8 Safety and Reactogenicity

Safety will be monitored by performing physical examinations including vital signs, routine laboratory measurements as well as by evaluating local and general solicited AEs and unsolicited AEs.

### 8.1 Definitions

#### 8.1.1 Medical History

Symptoms present before or at the Screening Visit will be documented in the medical history.

#### 8.1.2 AEs

AEs are defined as any untoward (undesirable) occurrence of a medical event in a clinical trial subject temporally associated with the administration of an IMP or a medicinal product (MP) which does not necessarily have a causal relationship with this IMP/MP. Any new signs, symptoms or changes in health starting after ICF signature are documented in the subjects' records and the AE section of the eCRF (data collection requirements for screen failures see [Section 12.1](#)). AEs are recorded based on unsolicited and solicited questioning ([Section 8.1.2.1](#) and [8.1.2.2](#)).

##### 8.1.2.1 Unsolicited AEs

Unsolicited AEs are defined as AEs observed by the subject/investigator or which are not pre-listed on the memory aid card. AEs (e.g. feeling of ill-health, subjective symptoms and objective signs, intercurrent diseases, accidents, etc.) observed by the investigator and/or reported by the subject must be recorded in the eCRF regardless of the assessment of causality in relationship with the IMP/MP.

After the first vaccination, abnormal laboratory values assessed as being clinically significant by the investigator are to be documented as AEs. In addition, after first vaccination, abnormal laboratory values fulfilling the Grade 3 or Grade 4 criteria according to the toxicity scale ([Appendix 1: Toxicity Scale for Laboratory Values](#)) are to be documented as AE in the eCRF, regardless of whether they are considered clinically relevant or not. For lab values fulfilling the Grade 3 or Grade 4 criteria, the decision to repeat the labs is left at the discretion of the PI. Toxicity grade and seriousness of an AE will be assessed separately, i.e. a Grade 3 or Grade 4 AE will not automatically be regarded as serious.

The investigator should ask the subjects if they have experienced any AEs since their last visit. All intercurrent diseases reported by the subject need to be recorded by the investigator in the appropriate section of the eCRF.

Any adverse events starting during the screening phase, i.e. after informed consent is given but before the first vaccination, are considered as pre-treatment adverse events.

### **8.1.2.2 Solicited AEs**

In this clinical trial protocol solicited AEs are defined as all symptoms specifically listed in the memory aid provided to the subjects following each vaccination. After vaccination the subjects are requested to monitor and record local symptoms (i.e. erythema, swelling, induration, pruritus and pain at the injection site) as well as general symptoms (i.e. body temperature, headache, chills, myalgia, nausea and fatigue) in the memory aid daily for the day of vaccination and the following 7 days (Days 0-7, 8 day period).

### **8.1.2.3 SAEs**

A SAE is any untoward medical occurrence that at any dose:

- Results in death
- Is life-threatening

The term “life-threatening” in the definition of “serious” refers to an event in which the patient was at risk of death at the time of the event; it does not refer to an event which hypothetically might have caused death, if it were more severe.

- Requires in-patient hospitalization or prolongation of existing hospitalization
- Results in persistent or significant disability or incapacity
- Results in a congenital anomaly or birth defect
- Is an otherwise important medical event, e.g. leads to suspicion of transmission of an infectious agent.

Medical and scientific judgment should be exercised in deciding whether expedited reporting is appropriate in other situations, such as important medical events that may not be immediately life-threatening or result in death or hospitalization but may jeopardize the subject or may require intervention to prevent one of the other outcomes listed in the definition above. These should also usually be considered serious.

Examples of such events are intensive treatment in an emergency room or at home for allergic bronchospasm; blood dyscrasias or convulsions that do not result in hospitalization; or development of drug dependency or drug abuse.

## 8.2 Assessment

### 8.2.1 Relevant Medical History

Relevant medical history will be documented at screening and will focus particularly on any important diseases and in case of infections or tumors, the pathogen involved or the pathological diagnosis, if available. Special attention should be given to history of prior allergic reactions, especially to vaccines.

### 8.2.2 Prior and Concomitant Medication

Exclusionary medication or medication where washouts periods need to be adhered to are defined in the eligibility criteria in [Section 1.5](#).

All concomitant (ongoing) medication except homeopathic substances and dietary supplements must be recorded in the eCRF and the subject's medical record including information about the indication, dosage regimen, and the onset and end of treatment.

The following medication, taken within 3 months prior to screening or BV0, will also be recorded in the eCRF and the subjects medical record: vaccines (e.g. Influenza/Pneumococcal), corticosteroids (via any route of administration), other immune-modulating drugs, immunoglobulin and/or any blood products, investigational drugs and depot preparations which are still active at the date of screening.

If given after the first but prior to the second or the booster vaccination, the following will result in subject's ineligibility to receive the second or booster vaccination and the subject should follow the abbreviated visit schedule (see [Section 4.2.4](#))

- Vaccination with any licensed live vaccine within 30 days prior to or after trial vaccination or any licensed inactivated vaccine within 14 days prior to or after trial vaccination.
- Start of chronic systemic administration (defined as more than 14 days) of > 5 mg prednisone (or equivalent) per day or any other systemic use of immune-modifying drugs.
- Administration of immunoglobulins and/or any blood products.

- Use of any investigational or non-registered drug or vaccine other than the trial vaccine.

### **8.2.3 Physical Examination**

#### Complete physical examination

A complete physical examination will be performed at screening and BV0. The examination includes a review of major organ systems as well as body height and weight. The examination should be directed at finding evidence of any infections, tumors and lymphadenopathy (a grading scale for lymphadenopathy is included in [Appendix 3: Grading Scale for Lymphadenopathy](#)). In addition, auscultation of the heart and lungs will be performed to check specifically for signs of any heart condition.

#### Targeted physical examination

In the main trial, a targeted physical examination, guided by any signs or symptoms previously identified or any new symptoms that the subject has experienced since the last visit, is required at all visits starting at Visit 1 except VS.

In the booster substudy, a targeted physical examination will only be performed if clinically indicated, by the presence of signs/symptoms since last visit at BV1 to BFU2. If performed, auscultation of the heart and lungs will be included.

### **8.2.4 Vital Signs**

At all visits except the Staggering Visit and BFU3, blood pressure and pulse rate will be taken after the subject has been sitting upright for approximately two minutes. Body temperature will be measured orally.

### **8.2.5 Unsolicited AEs**

All intercurrent diseases reported when the investigator actively inquires the subject will be documented and all required details (e.g. start and stop date, intensity) will be assessed. Unsolicited AEs will be reported in the respective section of the eCRF and the subject's medical record (requirements for screen failures see [Section 12.1](#)).

Unsolicited AEs will be assessed and documented as indicated in the trial schedule (see [Section 1.6](#) and [Section 1.7](#)).

SAEs will be assessed and documented at all trial visits, excluding the BFU3 Visit. SAEs will be followed up until resolution or achievement of stable clinical conditions.

In the main trial, new AEs related to respiratory tract infections will be assessed and documented at all trial visits, including the FU Visits.

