Examination of injection site			◆	■				

■ = mandatory; □ = in case of medical need or any underlying condition that requires further examinations; ◆ = PBMC Subgroup only

 Review of acceptable contraceptive methods and recent menstrual history with WOCBP.

 New SAEs and changes to AEs/SAEs ongoing at the previous visit only.

 Urine pregnancy test

 Additional safety measures can be taken at any other trial visit or at unscheduled visits, if clinically indicated.

 Approximate amounts of single blood draws: Safety lab: 11 mL (at BV0 and BV2; BFU1and BFU2 if applicable), including Haematology (3 mL), serum chemistry (including pregnancy test; 8 mL); serum collection (antibody testing): 9 mL; PBMC collection (T cell collection): 64 mL.

 The memory aid should be completed daily for an 8-day period (Day 0 to Day 7), starting with the day of vaccination. If symptoms are ongoing after Day 7, temperature/symptom measurements should continue each day until resolved and the last day of the symptom and maximum intensity will be recorded on the memory aid.

 The entries on the memory aid card need to be reviewed together with the subject.

 PBMC subgroup only.

 Refer to [Section 8.2.9](#) for Cardiac Assessment

 Nasal swabs will be taken from both nostrils.

 BV1 approximately 11-13 months after the first vaccination in the main part of the trial

 A targeted physical examination is only needed if guided by any signs or symptoms previously identified or any new symptoms that the subject has experienced since the last visit

 Concomitant medication at BFU visits are only to be captured in case the concomitant medication is related to a new SAE and changes to AEs/SAEs ongoing at the previous visit

 Concomitant medication between FU2 and BV0 are only to be captured in case the concomitant medication is related to a SAE.

 At BFU3 only blood draw for immunogenicity serum collection will be performed (9 mL)

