#### 4.2.2.3 Booster Follow-Up (BFU) Phase

To monitor long-term safety and antibody persistence, subjects will come to the CTS for follow-up (FU) visits 3 months (BFU1 Visit), 6 months (BFU2 Visit) and 12 months (BFU3 Visit) after the booster vaccination.

Booster FU1 Visit (BV1 + 84-98 days)
The following tasks will be performed:

• Recording of new SAEs and changes to AEs /SAEs ongoing at last active trial Visit BEAP

• Evaluation of vital signs

• Recording of concomitant medication for ongoing AEs/SAEs since BEAP or new SAEs

• Blood draw for serum collection (9 mL)

• Nasal swab collection for mucosal immune response (swabs are taken from both nostrils)

Only for the subgroup: PBMC collection (64 mL)
Only if clinically indicated:

• Blood draw for safety laboratory (hematology & serum chemistry, 11 mL)

• Targeted physical examination (see Section 8.2.3)

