## 8.3 Reporting

### 8.3.1 Reporting of SAEs

All SAEs occurring throughout the entire course of the trial have to be reported to the CRO Drug Safety (DS) Department. The CTS has to send the completed SAE form by e-mail or fax to the CRO DS Department within 24 hours of becoming aware of the AE.

SAE should be sent to:

[figure not shown]

The investigator should not delay reporting because of missing information. Nonetheless, the report should be as complete as possible. This initial notification should include, as a minimum, sufficient information to permit identification of the following:

- the reporter (investigator's name and contact information)
- the subject
- involved trial medication
- AE(s)
- seriousness criterion
- date of onset

The CRO DS Department alerts BN PV of all SAEs and provides the available information within 24 hours to BN PV. BN is responsible for expedited as well as periodic reporting to the involved regulatory authorities (e.g. Food and Drug Administration, European Medicines Agency (EMA), Paul Ehrlich Institut [PEI]) according to applicable laws and guidelines. Regulatory authorities will be notified as soon as possible but no later than 7 days after first knowledge of a fatal or life-threatening unexpected SAE with an at least possible relationship to the IMP (SUSAR) and no later than 15 days after knowledge of any other unexpected SADR. The investigator or the CRO is responsible for reporting to the Ethics Committees or IRBs. [Figure 4](#) outlines the reporting process and timelines for SAEs.

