## **Booster Follow-Up Trial Phase**

Time period between the BEAP and the final study visit. Note that for subjects who do not return for booster sub-study follow-up visits (BFU), there may be no BFU phase data available.

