### **Serious Adverse Events**

All Serious Adverse Events (SAEs) from BV1 to the last follow-up visit are considered as treatment-emergent, regardless of the day of onset.

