### **Serious Adverse Events**

All SAEs (solicited and unsolicited) with onset from booster vaccination up to and including BEAP will be summarized by SOC and PT. Related SAEs and SAEs which occurred during the BFU Phase will be presented in a similar fashion.

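### Active SAE questioning after the booster stops at BFU2, but the protocol and booster SAP carry SAE reporting and counting to the final visit six months later

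*Protocol*

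**What the plan says.** **Where SAE questioning stops.** Protocol 8.2.5: "SAEs will be assessed and documented at all trial visits, excluding the BFU3 Visit". The booster schedule (Protocol 1.7) has no AE/SAE mark under BFU3, and its footnote 15 reads "At BFU3 only blood draw for immunogenicity serum collection will be performed (9 mL". The BFU3 task list in 4.2.2.3 contains that one task. The last visit with SAE recording is BFU2.

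**Where SAE reporting and counting stop.**
- Protocol 8.3.1: "All SAEs occurring throughout the entire course of the trial have to be reported to the CRO Drug Safety (DS) Department". It makes no exception for the period after BFU2.
- Protocol 4.2.2.3: "To monitor long-term safety and antibody persistence, subjects will come to the CTS for follow-up (FU) visits 3 months". The sentence goes on to name the 6-month and 12-month visits, BFU2 and BFU3.
- Booster SAP, General Definitions: "All Serious Adverse Events (SAEs) from BV1 to the last follow-up visit are considered as treatment-emergent, regardless of the day of onset".
- Booster SAP, definition of the booster follow-up phase: "Time period between the BEAP and the final study visit".
- Booster SAP 4.5.8: "Related SAEs and SAEs which occurred during the BFU Phase will be presented in a similar fashion". No cut-off at BFU2 is given.

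The SAE endpoint in booster SAP 2.6.2 has no time limit. The tables in Appendix 6.3 that summarise SAEs by system organ class (15.3.2.1 and 15.3.2.2) are both confined to the booster active trial phase.

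**The concern.** The rules for reporting, classifying and presenting SAEs run to the last visit, while the rule for asking about them ends one visit earlier. A subject admitted to hospital at month 8 would come in at month 12, give blood, and not be asked. Whether that admission reaches the database depends on the site hearing of it some other way.

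Safety after the booster is a stated secondary objective, and the SAP attaches no label and no separate observation period to the time after BFU2. A reader who sees SAEs defined from the booster vaccination (BV1) to the last follow-up visit will assume the same ascertainment throughout. If events are missed, the bias is towards fewer SAEs after repeat dosing.

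**Working it through.** The documents state no figure for SAE follow-up, so the check sets the rules side by side and sizes the interval from the visit windows.

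**Timeline check.** Baseline of 28 days plus BFU3 at day 364 gives 392 days; 392 / 7 = 56 weeks. This matches the booster duration in Protocol 4.3, so the stated duration includes BFU3. The booster SAP is written to Edition 4.0 and tabulates BFU3 attendance (4.5.3), so its last follow-up visit is BFU3.

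**Inputs.** BFU2 is at day 182-210 (week 26) and BFU3 at day 364-392 (week 52), from Protocol 1.7. 86 subjects are to be followed for 12 months (Protocol 1.5).

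**Length of the gap.**
- Nominal: 52 - 26 = 26 weeks; 26 / 52 = 50% of post-booster follow-up.
- Shortest by the windows: 364 - 210 = 154 days; 154 / 364 = 42%.
- Longest by the windows: 392 - 182 = 210 days; 210 / 392 = 54%.

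**Person-time, no dropout.**
- Nominal: 86 x 26 / 52 = 43 person-years.
- Range: 86 x 154 / 365.25 = 36 to 86 x 210 / 365.25 = 49 person-years.

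**Expected SAEs in the gap.** The documents give no SAE rate, so these rates are assumptions. Expected number = rate x 43; chance of at least one = 1 - exp(-expected).

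| Assumed rate per person-year | Expected SAEs | Chance of at least one |
|---|---|---|
| 0.02 | 0.02 x 43 = 0.9 | 58% |
| 0.05 | 0.05 x 43 = 2.2 | 88% |
| 0.10 | 0.10 x 43 = 4.3 | 99% |
| 0.20 | 0.20 x 43 = 8.6 | over 99.9% |

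These are SAEs occurring while nobody is scheduled to ask about them. They are not a count of missed SAEs, because some would still be reported under 8.3.1.

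**Text against tables.** SAP 4.5.8 says follow-up-phase SAEs will be presented in the same way as the active-phase summary. Appendix 6.3 lists no such table, so on the current list they would appear only in the SAE listings.

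**The case against.** The strongest reply is that BFU3 was deliberately made a serology visit. Amendment 3 adds it for antibody durability. Vital signs (8.2.4), targeted examination (8.2.3), SAE assessment (8.2.5), the schedule and the task list all leave it out consistently. The abbreviated schedule after early discontinuation (4.2.4) also ends at BFU2. Six months of active SAE follow-up after the last dose matches the main trial. The purpose sentence in 4.2.2.3 covers three visits jointly and need not mean that each serves both aims. The SAP's treatment-emergent rule can be read as a label for whatever SAEs arrive, not as a promise of solicited follow-up.

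Much of this stands as an account of intent, but it does not reconcile the text. If collection was meant to end at BFU2, then 4.2.2.3, 8.3.1, the two SAP definitions and SAP 4.5.8 should say so. The same amendment also gives the added BFU3 visit as its reason for adding the booster safety objective.

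Three stronger readings are tempting, and the documents do not support them.
- *Months 6 to 12 are event-free by construction.* They are not. Section 8.3.1 obliges sites to report any SAE within 24 hours of becoming aware of it. Section 8.2.5 adds, for SAEs already known, that "SAEs will be followed up until resolution or achievement of stable clinical conditions". Ascertainment is passive, not absent.
- *A death would show only as a missed BFU3.* SAP 4.5.3 tabulates reasons for withdrawal from the follow-up phase, and a death known to the site is reportable under 8.3.1.
- *The report will show a 12-month SAE count diluted by unasked time.* The listed SAE tables cover only the active phase, and the SAP defines no SAE rate or person-time denominator.

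**Conclusion.** The inconsistency is real and is in current text. From BFU2 to BFU3, about half of post-booster follow-up (42% to 54% by the windows, about 43 person-years, range 36 to 49), SAEs are captured passively and incompletely, while other passages carry SAE reporting and counting through to the end. The person-time assumes all 86 subjects are boosted and none drop out. The expected 0.9 to 8.6 SAEs rest wholly on the assumed rates of 2 to 20 per 100 person-years, and the share that would reach sites unprompted is unknown. What follows is limited: few or no reports from this period would be weak evidence of few or no events, and nothing in the SAP warns the reader of that. The point is worth correcting because the SAE endpoint has no time limit and the correction is small.

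**What to change.** Preferred: add an item to BFU3 for recording SAEs since BFU2, with any concomitant medication related to an SAE. Enter it in Protocol 1.7 (including footnote 15), 4.2.2.3 and 8.2.5, and remove the BFU3 exception from 8.2.5. The protocol already has a model: BV0 asks for SAEs since the last main-trial follow-up visit. BV0 precedes a dose and BFU3 does not, so the safety purpose differs, but the question carries over directly. The cost is a minor amendment, one eCRF line, one question at a visit the subject already attends, and possibly a few extra SAE forms.

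Alternative, if active collection is meant to end at BFU2: say so in Protocol 4.2.2.3 and 8.3.1, in the SAP definitions of SAEs and of the booster follow-up phase, and in SAP 4.5.8. Keep later SAEs reportable, label them as spontaneously reported, and end the SAE observation period at BFU2. Do not simply cut the SAP's treatment-emergent definition at BFU2: that would strip the label from SAEs which 8.3.1 still requires and leave the conflict in place. The cost is wording only.

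In either case, align SAP 4.5.8 with Appendix 6.3 by adding a follow-up-phase SAE table or by stating that these SAEs are only listed.
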